### **4.4.2 Prohibited Medications/Treatments**

Subjects must not initiate or be on an existing regimen of anti-coagulant medications (eg, warfarin, clopidogrel) or other medications or substances known to increase coagulation time (eg, aspirin, ibuprofen, or herbal supplements) in the 10 days prior to undergoing study device injection and for 3 days afterward.

During the course of the study, subjects must not:

- be enrolled in another study and may not receive another investigational product in the 30 days prior to study enrollment
- receive permanent facial implants (eg, polymethylmethacrylate, silicone, polytetrafluoroethylene) anywhere in the face
- receive facial tissue augmentation with fat injections above the subnasale; semi-permanent dermal fillers (eg, calcium hydroxyapatite, poly-L-lactic acid) in the temple or midface; or dermal filler injections
- receive botulinum toxin injections above the subnasale
- undergo mesotherapy or receive cosmetic facial procedures (eg, face-lift, brow lift, facial reconstructive surgery, laser, photomodulation, intense pulsed light, radio frequency, dermabrasion, moderate or greater depth chemical peel, or other ablative procedures) anywhere in the face
- undergo allergen desensitization therapy
- undergo any piercing or tattooing procedures above the subnasale

The use of hyaluronidase for aesthetic purposes (eg, to reverse overcorrection) is not permitted.

The decision to administer a prohibited medication/treatment is done with the safety of the study participant as the primary consideration. When possible, Allergan is to be notified before the prohibited medication/treatment is administered.

#### **4.4.3 Special Diet or Activities**

Within the first 24 hours after treatment, it is recommended that subjects avoid strenuous exercise, extensive sun or heat exposure, and alcoholic beverages. Exposure to any of the above may cause temporary redness, swelling, and/or itching at the injection sites.

For 2 days after treatment, it is recommended that subjects avoid unnecessary external compression of the treatment site that could cause displacement or indentation where the product has been placed.

For 1 week after treatment, subjects will be advised not to have a massage, enter a hot spring or sauna, or go swimming.

For 3 months after treatment, it is recommended that subjects not wear tight-fitting swim goggles.

#### **4.5 Treatment Allocation Ratio**

Subjects are randomized at an allocation ratio of 3:1 to treatment with VOLBELLA XC or no treatment control group.

### **5. Study Population**

#### **5.1 Number of Subjects**

Up to 175 subjects will be enrolled at up to 15 sites in order to randomize 140 subjects and have an estimated 112 subjects complete the study based on an anticipated 20% screen fail rate and dropout rate of 20% during the study.

## 5.2 Study Population Characteristics

Adult subjects with infraorbital hollowing who are seeking restoration will be recruited. The randomization target is a minimum of 18 subjects of Fitzpatrick skin phototypes I/II, 18 of phototypes III/IV, and 18 of phototypes V/VI.

## 5.3 Inclusion Criteria

The following are requirements for entry into the study:

1. Age 22 or over and in good general health
2. Has “Moderate” or “Severe” infraorbital hollowing (grade 2 or 3 on the AIHS) for each eye as assessed by the EI (ie, both eyes must qualify but do not need to have the same score)
3. TI considers the subject’s anatomy to be amenable to improvement to an AIHS grade of 0 or 1 (None or Minimal)
4. Is able to complete effectiveness self-assessments without the use of glasses (contact lens use is acceptable if they will be used for all subject self-assessments)
5. Ability to follow study instructions and likely to complete all required visits
6. Written informed consent has been obtained

## 5.4 Exclusion Criteria

The following are criteria for exclusion from participating in the study:

1. Has atrophic skin in the tear trough region as determined by the TI
2. Has large lower lid fat pads that would mask improvement, as determined by the TI
3. Has hyperpigmentation in the infraorbital area (does not include dark circles under the eyes not due to hyperpigmentation)
4. Has significant volume loss in the midface
5. Has a cornea that projects farther forward than the most anteriorly projected part of the cheek
6. Has ever received permanent facial implants (eg, polymethylmethacrylate, silicone, polytetrafluoroethylene) anywhere in the face or neck, or is planning to be implanted with any of these products during the study
7. Has ever undergone fat injections above the subnasale or is planning to undergo this procedure during the study
8. Has tattoos, piercings, facial hair (ie, beard, mustache), or scars that would interfere with visual assessment of the infraorbital hollows

9. Has undergone volume augmentation with semipermanent dermal fillers (eg, calcium hydroxyapatite, poly-L-lactic acid) or temporary dermal fillers in the malar area, temples, or around the eyes within 12 months before enrollment or is planning to undergo such treatment during the study
10. Has active or recurrent inflammation or infection in either eye
11. Has ever received a blepharoplasty, facelift, browlift, or is planning to during the study
12. Has undergone mesotherapy or cosmetic treatment (laser, photomodulation, intense pulsed light, radio frequency, dermabrasion, moderate or greater depth chemical peel, liposuction, lipolysis, or other ablative procedures) anywhere in the face or neck or botulinum toxin injections above the subnasale within 6 months before enrollment or is planning to undergo any of these procedures during the study
13. Has experienced trauma to the infraorbital area within 6 months before enrollment or has residual deficiencies, deformities, or scarring in the periorbital or cheek areas
14. Has a tendency to develop hypertrophic scarring
15. Has a history of anaphylaxis or allergy to lidocaine (or any amide-based anesthetics), hyaluronic acid products, or Streptococcal protein, or is planning to undergo desensitization therapy during the term of the study
16. Has active autoimmune disease
17. Has current cutaneous or mucosal inflammatory or infectious processes (eg, acne, herpes, gum disease), abscess, an unhealed wound, or a cancerous or precancerous lesion, above the subnasale
18. Has received any investigational product within 30 days prior to study enrollment or is planning to participate in another investigation during the course of this study
19. Has begun using any new over-the-counter or prescription oral or topical, anti-wrinkle products within 30 days before enrollment or is planning to begin using such products during the study (subjects who have been on a regimen of such products for at least 30 days are eligible for the study if they intend to continue their regimen throughout the study)
20. Females who are pregnant, nursing, or planning a pregnancy
21. Is an employee (or a relative of an employee) of the TI, EI, or Allergan, or a representative of Allergan
22. Has a condition or is in a situation which in the TI's opinion may put the subject at significant risk, may confound the study results, or may interfere significantly with the subject's participation in the study

## 6. Procedures

### 6.1 Washout or Run-In Intervals

#### 6.1.1 Washout Intervals

Washout Intervals	Medication or Procedure
10 days before treatment	
 
Ongoing regimen of medications and/or substances known to increase coagulation time (eg, aspirin, ibuprofen, or herbal supplements)
 
 
NOTE: The 10-day washout period for anticoagulants must continue for 3 days after treatment (initial, touch-up, and repeat) is administered

30 days before enrollment	
 
Any investigational product
 

#### 6.1.2 Run-in Intervals

Run-in Intervals	Medication or Procedure
30 days before enrollment	
 
Over-the-counter or prescription, oral or topical, anti-wrinkle products above the subnasale for subjects who will use such products during the study
 

## 6.2 Procedures to be Performed

The TIs will be trained in the injection technique, and TIs and EIs will be trained in the use of the AIHS prior to initiating enrollment.

Throughout the study, to the extent possible, it is recommended that treatment and safety assessments for a particular subject be performed by the same TI, and effectiveness assessments (AIHS and Global Aesthetic Improvement Scale [GAIS]) be performed by the same EI. If it is not possible to use the same evaluator to follow the subject, it is recommended that evaluations overlap (examine the subject together and discuss findings) for at least 1 visit.

At each visit and safety telephone call, the TI (or designee) will solicit and record information about adverse events (AEs) and concomitant medications, therapies, and treatments. The TI (or designee) will begin by asking the subject a general, non-directed question, “How have you been feeling since the last visit?” Directed questioning and examination will then be done as appropriate and may include referral to a retinal specialist.

Any subject with any ophthalmic signs and symptoms or vision loss will be referred immediately to a retinal specialist for an examination. All reported AEs will be documented.

### **6.2.1 Screening Visit**

At the screening visit, the TI (or designee) will discuss routine alternative treatments that may be available with any subject who is interested in participating in the study. The available alternative treatments include plastic surgery, autologous fat injection, etc; he/she will counsel the subject regarding his/her treatment goals, and the potential benefit and limitations of study treatment. After counseling, if the subject's expectations are not realistic, the TI (or designee) will not proceed with obtaining the subject's signature on the Informed Consent Form (ICF) and will discontinue the subject from the study.

A subject is considered enrolled when he/she has signed the ICF in the presence of the TI or a qualified designee. The site will then log onto the interactive web response system (IWRS) to obtain a unique subject number that will serve as the subject identification number on all study documents.

The TI (or designee) will collect and record the subject's demographic information, medical and surgical history, cosmetic and dental procedure history, smoking history, Fitzpatrick skin phototype, and sun exposure estimate. Physical measurements (height and weight) and vital signs, including blood pressure (systolic and diastolic, while subject is seated), temperature, pulse, and respiratory rate will also be collected and recorded. A urine pregnancy test will be conducted for female subjects of childbearing potential. If the test is positive, the subject will be exited from the study.

The EI will evaluate the subject's infraorbital hollowing for each side using the AIHS. Subjects who have an AIHS score of "Moderate" or "Severe" for each infraorbital hollowing will be eligible for the study. Although both infraorbital hollows must qualify, each infraorbital hollow can have a different score (eg, 1 eye can be "Moderate" and the other "Severe").

The TI will ensure that each subject meets the study eligibility criteria and run-in and washout requirements (see [Sections 5.3](#), [5.4](#), and [6.1](#)). The TI will record the reasons for those subjects who do not meet the inclusion/exclusion criteria and who withdraw consent before randomization.

The schedule of procedures to be conducted at screening are provided in [Table 1](#) and [Table 4](#).

## 6.2.2 Randomization Visit

The randomization visit may occur on the same day as the screening visit and must occur within 30 days after screening/signing of the ICF. Before randomization, subjects will undergo [REDACTED] imaging. [REDACTED]

[REDACTED] Inclusion/exclusion criteria will be reviewed again to confirm subject eligibility. Female subjects of childbearing potential will take a urine pregnancy test; if the test is positive, the subject will not receive treatment and will be exited from the study.

Subjects will be randomized in a 3:1 ratio to the treatment group or to the control group and 1:1 to receive the first treatment in the right or left side. The same order must be used for all treatments. Subjects randomized to the treatment group will complete the validated FACE-Q Appraisal of Lower Eyelids questionnaire and have vision safety assessments performed by the TI. Subjects randomized to the control group will have no additional required procedures for the randomization visit.

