Study design: This is a prospective, multicenter, evaluator-blinded, randomized, controlled study to evaluate the safety and effectiveness of VOLBELLA XC hyaluronic acid (HA) injectable gel to correct infraorbital hollowing. Once screened, subjects will be randomized to either the treatment or control group. The treatment group will receive treatment at the start of the study and an optional touch-up treatment 1 month later. They will be followed for safety and effectiveness for 12 months with the option for a repeat treatment and an additional month of follow-up. The control group will complete a 3-month control phase after randomization and will be offered optional treatment and optional touch-up treatment 1 month later. They will be followed only for safety for 9 months. At screening, after written informed consent has been given, the Treating Investigator (TI) will document the subject's demographics, height, weight, vital signs, Fitzpatrick skin phototype, and history of sun exposure, smoking, and medical, surgical, dental, and cosmetic procedures. Female subjects of childbearing potential will undergo urine pregnancy tests. The Evaluating Investigator (EI) will rate subjects on the 5-point photonumeric Allergan Infraorbital Hollows Scale (AIHS) to determine eligibility for the study. The TI will ensure the subject's anatomy is amenable to correction to an AIHS rating of 0 or 1 [REDACTED]. Before randomization, subjects will undergo [REDACTED]. All subjects will be randomized 3:1 to the treatment group or the control group, and will also be randomized 1:1 to receive the first treatment on the right or left side. The same order must be used for all treatments. Treatment group: Before treatment, subjects randomized to the treatment group will complete the following assessments: 

• FACE-Q Appraisal of Lower Eyelids questionnaire

• TI (or designee) safety assessments

○ Snellen visual acuity using a Snellen eye chart

○ confrontational visual fields

○ ocular motility

 The TI will use supplied 32G ½" needles or 27G 1½" cannulas (as provided by Allergan) based on the TI's preference to inject VOLBELLA XC submuscularly/supraperiostally to correct infraorbital hollowing. Topical or local anesthesia or ice will be applied as necessary. [REDACTED]. The following assessments will be performed on the treatment day after treatment: 

• TI assessments

○ product moldability

○ Snellen visual acuity ([REDACTED])

○ confrontational visual fields ([REDACTED])

○ ocular motility ([REDACTED])

○ adverse events (AEs)

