  - [REDACTED]
  - improvement in the infraorbital hollows using the GAIS (Months 1 and 3 only)

After the Month 3 procedures are complete, subjects will be offered optional treatment and will be followed for safety only for 9 months after last treatment. Control group subjects who decline optional treatment will exit the study after the Month 3 visit procedures are complete.

The optional treatment visit for the control group will be identical to the treatment visit for the treatment group. Control subjects who receive treatment will follow the same follow-up visit schedule as the treatment group, including optional touch-up, for 9 months after last treatment; however only the following assessments will be performed at follow-up visits:

- [REDACTED]
- TI (or designee) safety assessments:
  - Snellen visual acuity [REDACTED]
  - confrontational visual fields [REDACTED]
  - ocular motility [REDACTED]
  - AEs
  - recording of concomitant medications and procedures

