#### **4.3.3 Methods for Blinding**

The Evaluating Investigator (EI) and the image analysis technician will be blinded to treatment. The EI will not be present during the injection procedures. As the image files will be accessed by the blinded image analysis technician, the image files will not reveal subject treatment randomization or the timepoint at which the image was captured.

The Treating Investigators (TIs), study coordinators, and subjects will not be blinded to treatment, but they will secure the randomization and other records (eg, records of study treatments and prior study assessments) from potential discovery by the blinded EI. The TI will not discuss the randomized treatment assignments with or in the presence of the EI.

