Control group: Participants randomized to the control group will complete a 3-month no-treatment control period with office visits at Months 1 and 3. At randomization and at each of these office visits, the following assessments will be performed:

- AEs
- recording of concomitant medications and concurrent procedures
- EI effectiveness assessments
 - AIHS
 - [REDACTED]
 - improvement in the infraorbital hollows using the GAIS (Months 1 and 3 only)
- EI safety assessments
 - presence or absence of Tyndall effect [REDACTED]

After the Month 3 procedures are complete, participants will be offered optional treatment and will be followed for safety only for 9 months after last treatment. Control group participants who decline optional treatment will exit the study after the Month 3 visit procedures are complete.

The optional treatment visit for the control group will be identical to the treatment visit for the treatment group. Control participants who receive treatment will follow the same follow-up visit schedule as the treatment group, including optional touch-up, for 9 months after last treatment; however, only the following safety assessments will be performed at follow-up visits:

- [REDACTED]
- TI (or designee) safety assessments
 - Snellen visual acuity [REDACTED]
 - confrontational visual fields ([REDACTED])
 - ocular motility [REDACTED]

- AEs
- Recording of concomitant medications and procedures
- EI safety assessments
 - presence or absence of Tyndall effect [REDACTED]

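### An EI AIHS rating at randomization appears only in the control-group lists and conflicts with protocol section 6.2.2; done as listed, it could reveal controls to the blinded evaluator

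*Protocol*

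**What the plan says.** Four statements bear on the randomization visit.

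- **Controls, procedures section.** Protocol section 6.2.2 says: "Subjects randomized to the control group will have no additional required procedures for the randomization visit".
- **Controls, summary lists.** SAP section 4.1.1 introduces the control-group list with "At randomization and at each of these office visits, the following assessments will be performed", and the protocol synopsis uses the same sentence. The office visits meant are Months 1 and 3. Both lists contain the EI's AIHS rating. The only EI item with a visible time limit is the GAIS: "improvement in the infraorbital hollows using the GAIS (Months 1 and 3 only". The SAP list adds an EI check for Tyndall effect, part of whose wording is blacked out.
- **Treatment group, same day.** Section 6.2.2 says: "Subjects randomized to the treatment group will complete the validated FACE-Q Appraisal of Lower Eyelids questionnaire and have vision safety assessments performed by the TI". The synopsis introduces its matching list with "Before treatment, subjects randomized to the treatment group will complete the following assessments" and names FACE-Q and TI vision checks. SAP 4.1.1 agrees. None of these lists shows an EI rating.
- **All subjects.** At screening, section 6.2.1 provides: "The EI will evaluate the subject's infraorbital hollowing for each side using the AIHS". That screening rating is the baseline for the primary endpoint (protocol section 8.2.1, SAP Table 5-6).

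On blinding, protocol section 4.3.3 states: "The Evaluating Investigator (EI) and the image analysis technician will be blinded to treatment". Treating investigators, coordinators and subjects are not blinded.

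**The concern.** The primary endpoint is a subjective 5-point rating by the EI, compared between treated subjects and an untreated control group. Because everyone else knows the assignment, the comparison leans heavily on the EI not knowing it.

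The protocol already treats the pattern of EI contact as a blinding matter. Section 6.2.3.1 keeps the EI away from treatment procedures and from the Day 14 visit, and section 4.3.3 requires records of earlier assessments to be kept from the EI. A contact with the EI that happens after allocation in one group only would work against this. Section 6.2 recommends that the same EI follow a subject throughout, so the person who rated on the randomization day would normally also score Month 3.

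The rating brings no visible gain in return: with baseline fixed at screening, no visible analysis uses an AIHS score from the randomization day.

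**Working it through.** No figure in the plan depends on this point, so there is none to reproduce. The check is a comparison of the passages, followed by one illustrative calculation.

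**Comparison of the visible text for the randomization visit**

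| Source | Control | Treatment |
|---|---|---|
| Protocol synopsis | EI AIHS listed | FACE-Q, TI vision checks; no EI rating |
| SAP 4.1.1 | EI AIHS and Tyndall check listed | FACE-Q, TI vision checks; no EI rating |
| Protocol 6.2.2 | nothing beyond the common procedures | FACE-Q, TI vision checks; no EI rating |

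The control column disagrees with itself. The treatment column is consistent and shows no EI rating. Section 6.2.3.1 says that initial treatment should take place on the day of randomization, without the EI present. The next visible EI rating for treated subjects is Month 1 after the last treatment. No visible text places a randomization-visit rating before or after the allocation call.

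**What a rating request would tell the EI**

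Inputs: 140 subjects randomized (protocol section 5.1) and 3:1 allocation (section 4.5). Expected controls are 140 × 1/4 = 35, and expected treated subjects are 140 × 3/4 = 105.

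Suppose that every control is rated at the visit, and let f be the share of treated subjects also rated there. The documents give no value for f, so the values below are assumptions. By Bayes' rule,

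P(control | rated) = 0.25 / (0.25 + 0.75 f).

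- f = 0 (lists followed literally): 0.25 / 0.25 = 1.00
- f = 0.25: 0.25 / 0.4375 = 0.57
- f = 0.5: 0.25 / 0.625 = 0.40
- f = 1 (everyone rated, before allocation): 0.25 / 1.00 = 0.25

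At f = 1 the visit tells the EI nothing beyond the allocation ratio. At f = 0 each of the roughly 35 controls is identified by the request, and its absence would in principle point to the other 105 as treated.

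**Step that cannot be taken.** Going from a recognized control to a biased Month 3 score needs the EI's recall and its effect on the rating. The documents give neither.

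**The case against.** A reader might infer that the EI will be unblinded, or that the EI meets only controls after allocation. The documents do not support either reading.

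- **The lists are not exclusive or complete.** The control list also contains adverse events and concomitant medications, which section 6.2 requires for everyone at each visit. The synopsis pre-treatment list omits the pregnancy test that section 6.2.2 requires at that visit. An item's absence from the treatment list is therefore weak evidence that treated subjects are not rated.
- **Part of the text is hidden.** In section 6.2.2 the statement that controls have nothing additional is relative to the common pre-randomization steps. Some of those are redacted, next to the sentence "Inclusion/exclusion criteria will be reviewed again to confirm subject eligibility". If the hidden text has the EI rate every subject, the conflict and the unblinding risk both disappear. The schedules in Tables 1 and 4 are not in the text available for review and may settle the matter.
- **Timing is not stated.** Screening and randomization may fall on one day, and the screening AIHS is then itself a randomization-day rating, done in everyone.
- **The EI sees both groups later.** Both are rated at Months 1 and 3, so any asymmetry is confined to the randomization day.
- **SAP Table 6-3 is not proof.** Its row for the randomization day may only mark Day 1, which Table 6-1 sets as the randomization date for controls. Table 6-2 likewise has rows for treatment visits, from which the EI is absent.

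These points stand, and they limit the conclusion to a risk. They do not make the visible passages agree. Even if the rating is common to all subjects, two lists present it as a control-group procedure, and no visible text fixes its order relative to allocation. The amendment summary shows that Amendment 1 clarified the GAIS timing in this control list; the AIHS entry carries no such limit. The SAP repeats the synopsis wording, however, so it is not independent support.

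**Conclusion.** The conflict between the control-group lists (synopsis, SAP 4.1.1) and protocol section 6.2.2 is present in the visible text. If the rating is done as listed, it could show the EI which subjects are controls: up to about 35 of 140. That ceiling assumes that the rating follows allocation, that no treated subject is rated at the visit, and that the EI remembers the contact at Month 3 and draws the inference. If every subject is rated before allocation, nothing is revealed.

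Unblinding is therefore possible but not established, and no size can be given for any bias in the responder comparison. The responder calculation, sample size and significance level are not affected. The point is worth acting on because the trial depends on EI blinding and the correction is nearly free.

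**What to change.** Reconcile the control-group lists in the protocol synopsis and SAP section 4.1.1 with protocol section 6.2.2, in one of two ways:

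1. Remove the randomization time point from the EI items in both control-group lists, leaving Months 1 and 3.
2. If a second pre-treatment rating is wanted, state in all three places that the EI does it in every subject before the interactive web response system (IWRS) returns the allocation.

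Leave the randomization-day row in SAP Table 6-3, since it may serve as the Day 1 anchor for the control visit windows.

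The cost is a wording clarification in each document. The first option drops the listed control rating at that visit. The second fixes its place before allocation and, if treated subjects are not already rated there, adds one EI rating for each of them. Neither changes the sample size, the test or the baseline definition.
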